6.10.4 Reversal of Heparin Infusion with Protamine sulfate

Reversal of heparin by protamine sulfate is usually dosed at 1 mg of protamine sulfate for every 100 units of heparin that needs reversal. A simple method is to calculate the total amount of heparin given over the last two to three hours and divide by 100 to get the dose of protamine sulfate necessary to reverse the majority of the heparin effect. Example: If the patient receives 1200 units of heparin per hour then the total amount of heparin over two to three hours would be 2400 to 3600 units of heparin needing reversal. Reversal of the heparin effect would require approximately 24-36 mg of protamine sulfate. The ultimate decision on whether to reverse heparin with protamine sulfate and the dose chosen will be up to the clinicians at each clinical site based on the individual clinical scenario.

Medical professionals at each clinical site will have authority to emergently stop the study drug infusion if they feel there is an urgent or emergent clinical development related to the study drug such as a drug related SAE.

6.10.5 Heparin Induced Thrombocytopenia (HIT)

If HIT is suspected all heparin medications should be stopped immediately. The management of HIT or suspected HIT is covered in **Section 8.4**.

6.11 Inflammatory Biomarker Collection and Processing

hs-CRP blood levels will be drawn and processed by each site's clinical laboratory and the results of these tests will be documented in the database CRFs for each time point which will include time of enrollment, and post-enrollment days #2, 4, 6, and 10. As such, these values will be immediately available to the DSMB and Steering Committee during the interim analysis.

hs-CRP levels will be measured in the CSF as well. CSF will be sent to the local institution's lab for analysis of hs-CRP in the appropriate tube per the lab's standard procedure.

Additional blood and CSF (when a drain is present) will be drawn at enrollment and post-enrollment days # 2, 4, 6 and 10. The blood and CSF will be processed and stored locally and then shipped to the biomarker core lab for further planned biomarker analysis to be processed in a batch fashion after all samples have been collected. Currently the planned biomarkers to be analyzed include: IL-6, TNF- α , P-Selectin, ICAM-1, HMGB-1, and MRP 8/14.

Biomarker processing kits will be mailed to each site that will include instructions, transfer pipettes, shipping packaging, specimen box, pre-filled labels, and other supplies necessary to process blood to plasma and store them in the -70°C freezer. Each site will need to supply venipuncture supplies (needles, vacutainer tubes, or butterfly needles). Each site will also need to supply their own centrifuge, ice bucket, dry ice, and -70°C freezer space.

Collection of Biomarker Blood Specimens and Processing to Plasma:

1. **Collect 9-10 ml of venous blood** using a lavender top Vacutainer (EDTA). Mix according to standard guidelines. If collecting blood from an IV, PICC, or other line, make sure there are no medications hooked up to the line (such as heparin), if there are, temporarily turn off these infusions and waste at least 5 cc of blood prior to collecting the specimen. Turn infusions back on at the same rate following the blood draw.
2. **Within 30 minutes of the blood draw, centrifuge the tube for 10 min at 500g** (approx. 2,000 rpm in a standard centrifuge). If samples cannot be processed within 30 minutes, the tubes should be kept on ice until they can be centrifuged (*no more than 2 hours delay*). **Do NOT freeze the whole blood samples!** Heavily hemolysed or lipemic samples are to be avoided.
3. **Aspirate and aliquot the plasma.** Using a transfer pipette, transfer approximately 0.9-1.0 ml of plasma (supernatant) into each of five properly-

labeled cryovials. Avoid any contamination with RBCs or WBCs at the bottom of the centrifuge tube. Cryovial tube should be labeled with the subject's study ID#, study timepoint (example: baseline, post-enrollment day #, etc), date, and time of the blood draw.

4. **Freeze the plasma aliquots.** Place cryovials in appropriate freezer boxes. A -70°C freezer is preferred for long-term storage. If not immediately available, a regular -20°C can be used for short storage periods (< 1 week) before transferring the samples to a -70°C freezer. Make sure the Freezer boxes are properly labeled. Attempt to keep cryovials for the same subject located together in the same freezer box when possible.

Collection of Biomarker CSF specimens and Processing:

1. **Collect 9-10 ml of cerebrospinal fluid** using standard sterile technique in a plain red-top vacutainer tube.
2. **Within 30 minutes centrifuge the CSF for 10 min at 500g** (approx. 2,000 rpm in a standard centrifuge). If tubes cannot be centrifuged within 30 minutes the tubes should be kept on ice until they can be centrifuged (no more than 2 hours delay). **Do NOT freeze uncentrifuged CSF samples!**
3. **Aspirate and aliquot the CSF.** Using a transfer pipette, transfer approximately 0.9-1.0 ml of CSF supernatant into each of five properly-labeled cryovials. Avoid any contamination with cells at the bottom of the centrifuge tube. Cryovial tube should be labeled with the subject's study ID#, study timepoint (see above), date, and time of the CSF collection.
4. **Freeze the CSF.** Place cryovials in appropriate freezer boxes. A -70°C freezer is preferred for long-term storage. If not immediately available, a regular -20°C can be used for short storage periods (< 1 week) before transferring the samples to a -70°C freezer. Make sure the Freezer boxes are properly labeled. Attempt to keep cryovials for the same subject located together in the same freezer box when possible.

We plan for samples to be mailed from each site in two batches to the Core Biomarker Laboratory. Commonly one shipment will occur after 6 patients have been enrolled and one shipment will occur after the last patient at the site has completed the inpatient phase. Batch shipping procedures may be modified by the CCC as necessary without altering this protocol in the future.

Shipment of Biomarker Samples:

1. Samples need to be shipped to the biomarker core laboratory in the freezer boxes packed into a Styrofoam shipping box containing dry ice. Use an overnight carrier with overnight delivery. Do not allow samples to thaw under any circumstances! Please ship on a Monday-Wednesday. Do not ship on a Thursday, Friday, Saturday or Sunday to be sure there is someone to receive the samples when they arrive.
2. Shipping address:
Attn: [name]. / ASTROH Study
Research Operations Manager
Clinical Trials Unit
University of Louisville
[name]
[name]
T:[contact]
F:[contact] or [name]
[contact]
3. After receiving the shipment, the Styrofoam boxes will be immediately transferred to a -70°C freezer. Samples will be inventoried appropriately (Origin, type of sample, number of aliquots, sample Id number, location within the box and the freezer).
4. Samples will be kept at -70°C until ready to be assayed.

Plasma and CSF from all patients at all time points will be processed by the Core Biomarker Laboratory in a single batch fashion for all biomarkers being tested (except hs-CRP which will be performed at the local site clinical labs). This data will be associated with each patient's study ID# and time of collection. Biomarker lab personnel will remain blinded to treatment allocation. Unused specimens will be stored in a bio repository at the University of Louisville laboratory for up to 10 years after the completion of the study for potential future biomarker analysis without the need for additional informed consent or notification of study subjects at the discretion of the study leadership. Permission for the possibility of future genetic testing on the blood or plasma samples is included in the standard ASTROH informed consent document template provided to each study site.

Biomarker Assays:

A. CYTOKINES (IL-6, TNF α)

1. Plasma or CSF aliquots will be thawed, centrifuged at 10,000 x g for 5 minutes and the supernatants used to measure the concentrations of IL-6 and TNF α using Milliplex MAP Multiplex kits (EMD Millipore, Billerica, MA) according to the manufacturer's instructions. Samples will be assayed in duplicates.

B. ADHESION MOLECULES (sICAM1, P-SELECTIN)

1. Plasma or CSF aliquots will be thawed, centrifuged at 10,000 x g for 5 minutes and the supernatants used to measure the concentrations of sICAM1 and P-Selectin using Milliplex MAP Multiplex kits (EMD Millipore, Billerica, MA) according to the manufacturer's instructions. Samples will be assayed in duplicates.

C. OTHER INFLAMMATORY MARKERS (HMGB1, MRP8/14)

1. Plasma or CSF aliquots will be thawed, centrifuged at 10,000 x g for 5 minutes and the supernatants used to measure the concentrations of HMGB1 and MRP8/14 using appropriate ELISA kits (Biolegend, San Diego, CA). Samples will be assayed in duplicates.

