Peak and Overall Plasma and CSF levels of hsCRP at enrollment and, infusion days #2, 4, 6, and 10 compared between groups.

-SECONDARY CLINICAL EFFECT ENDPOINTS

Trail Making Test Parts A&B at 90 (± 10) days post enrollment.

MoCA at 1-year (± 30 days)

Center for Epidemiologic Studies Depression Scale (CES-D) at 90 (± 10) days post enrollment

Return to work status between groups at 90 (± 10) days

SECONDARY EXPLORATORY PRESPECIFIED BIOMARKER OUTCOMES

Plasma and CSF levels of IL-6, TNF- α , P-Selectin, sICAM-1, HMGB-1, MRP8/14 plasma levels at enrollment and infusion day #2, 4, 6, and 10

ADDITIONAL PRE-SPECIFIED

Rate of MoCA ≤ 20 between groups at the 90-day follow-up visit.

**EXPLORATORY
OUTCOME ANALYSES**

In-hospital incidence of any fever ($> 38.3^{\circ} \text{C}$; $\geq 101.0^{\circ} \text{F}$), Incidence of multiple fever episodes (≥ 3), and Mean Daily Fever Burden.

GCS and NIHSS at enrollment and infusion days # 2,4,6,10, discharge and 90 (± 10) days

MoCA at post-enrollment day #1, 6 and 10

Correlation analysis between MoCA scores and inflammatory biomarker levels with and without adjusting for hemorrhage burden (Hijdra Sum Score).

Incidence of moderate and severe Radiographic Cerebral Vasospasm based on a CTA, MRA, or Catheter DSA obtained between PBD # 6-12 as determined by an independent and blinded core imaging lab.

Incidence of TCD criteria for significant vasospasm (velocities $>200 \text{ cm/s}$ and / or MCA / ICA (Lindgaard) ratio >6)

Incidence of TCD criteria for absence of vasospasm (velocities $<120 \text{ cm/s}$)

Incidence of clinical vasospasm requiring rescue therapy (eg, pressors, endovascular treatment)

Incidence of "Delayed Cerebral Ischemia" defined as:

- Symptoms of neurological deterioration (e.g. hemiparesis, aphasia, decreased level of consciousness)
- Symptoms last for more than an hour
- Symptoms are not explained by other physiological processes (e.g., hydrocephalus, hypotension)

CT or MRI evidence of Vasospasm Related Cerebral Infarction on post-infusion (discharge) imaging as scored by an independent and blinded core imaging lab

Global outcome as measured between group ordinal regression analysis of the modified Rankin Scale score at 90-days and 1-year.
Return to work status between groups at 1-year.
Lawton IADLs at 90 (± 10) days
QOLIBRI-OS at 90 (± 10) days and 1-year.
Checklist Individual Strength-subscale Fatigue (CIS-f) at 90 (± 10) days
Barthel Index at 90 (± 10) days and 1-year

**INVESTIGATIONAL

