STUDY DRUG NAME
AND FORMULATION**

Unfractionated Heparin (UFH) intravenous solution at a concentration of 100 units per ml (25,000 to 50,000 units of heparin in 250 to 500 ml of 0.9% or 0.45% NaCl solution)

INTENDED USE

A prophylactic infusion of LDIVH for up to 14 days with prescribed escalated dosing until the goal aPTT value is achieved. The LDIVH infusion is intended to prevent cognitive deficits in modified-Fisher grade 3 and 4 aneurysmal subarachnoid hemorrhage survivors following endovascular coil embolization of the ruptured cerebral aneurysm. The LDIVH infusion is to be initiated 12 ± 4 hours after coiling of the aneurysm. The infusion will be started at 8 units/kg/hr (0.08 cc/kg/hr) and increased by 2 units/kg/hr every 12 hours until the goal aPTT is reached (typically 12 u/kg/hr) *Note: The goal aPTT is an institution specific aPTT value that correlates with an anti-Xa assay value of 0.1 – 0.3 IU/ml of heparin.*

STUDY SUCCESS

For the purposes of this trial, study success is defined as demonstrating a statistically significant improvement in the mean MoCA score for the LDIVH arm compared to the control arm of the study at the 90-day follow-up visit or a significant reduction in inflammatory biomarker levels in the LDIVH arm compared to the control arm. In addition, there can be no significant differences between groups in the rate of Major Bleeding or Clinically Relevant Non-Major Bleeding attributable to the LDIVH treatment.

PATIENT COMPLETION

Patient completion in the study occurs when the patient has completed his/her 1-year follow-up

visit and all case report forms (CRFs) and Imaging required by the Study Protocol have been completed OR the patient has withdrawn from the study or has been determined to be “Lost to Follow-up” and all available CRFs and Imaging have been collected and submitted to the University of Louisville. The primary endpoint is the 90-day follow-up visit and therefore the primary data-analysis will occur after this date.

**PRIMARY PRINCIPAL
INVESTIGATOR (PPI) /
SPONSOR**

[name]
Associate Professor of Neurosurgery
Chief, Vascular Neurosurgery
University of Louisville School of Medicine
Louisville, KY
[contact];
[contact]

**CO-PRINCIPAL
INVESTIGATORS (Co-PI)**

J. [name], PhD
Professor of Neurosurgery, Pathology & Physiology
University of Maryland Medical Center
Baltimore, MD

[name]
Professor and Vice Chair for Education
Department of Neurosurgery
Director, Cerebrovascular Surgery Program

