5.4 Study Drug Blinding Procedure

Physicians, residents, nurses, and clinical staff providing clinical care during the acute hospitalization of the study subjects will be aware of the treatment allocation (unblinded) and as a result will be monitoring for safety concerns related to prolongation of coagulation parameters (aPTT and anti-Xa), thrombocytopenia, bleeding, development of DVT or PE, or other AEs or that might be related to the patient's treatment allocation (LDIVH vs. SOC).

The investigational pharmacy at each site will properly label the study drug infusion bag with all of the information including patient name, site specific medical record number, study site ID#, study patient ID#, and study drug concentration.

The study team members conducting the neurological and cognitive assessments during the 90- day and 1- year follow-up visits will remain blinded to treatment allocation. The patients will be instructed not to reveal their treatment allocation. All imaging will be de-identified and coded in a HIPAA compliant manner with the patient's study ID # and date of scan but without any other information that would allow the core imaging lab to identify the patient identity, treatment allocation or dose. The biostatistician will be aware of two treatment groups but will not be aware of

whether the group was treated with UFH during interim analysis for the DSMB unless the DSMB determines it is necessary to unblind for safety purposes. The final statistical analysis will be performed in an unblinded fashion but rigorous methodology will be utilized. The study team members conducting imaging verification and the biostatistician will not have direct patient contact so accidental disclosure by the study subjects themselves should not occur.

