6.7 Baseline Blood And Biomarker Specimen Collection

Please draw all normal blood tests as you would for your normal standard of care for the treatment of an aneurysmal subarachnoid hemorrhage. hsCRP and Anti-Xa levels will be drawn for all subjects after enrollment but prior to initiation of the study drug (for those subjects in the LDIVH treatment group).

Additional blood will be drawn and processed to plasma and stored for additional biomarker analysis. This may be performed up to 6 hours after initiation of study drug for the LDIVH arm (but preferably prior to study drug initiation). Please see the section below on the collection and processing of plasma biomarker specimens Section 6.11

If the subject already has an external ventricular drain or a lumbar drain placed, then removal of cerebrospinal fluid should be performed again with processing of the specimens for biomarker analysis. This may be performed up to 6 hours after initiation of study drug for LDIVH arm (but preferably prior to study drug initiation). Please see the section below on the collection and processing of CSF biomarker specimens Section 6.11.

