9. CRITERIA FOR INTERVENTION DISCONTINUATION

9.1 TEMPORARY INTERRUPTION OF THE STUDY DRUG

It may become necessary to temporarily stop the study drug infusion during the course of this study.

- The attending physician investigator responsible for the patient will give permission to stop the study drug.
- For minor procedures not involving the CNS (e.g., tracheostomy, central line) the LDIVH infusion does not need to be stopped as long as the last set of coagulation labs were considered to be at a safe level to perform the procedure.
- For a minor procedure involving the CNS (e.g., ventricular drain, lumbar puncture, lumbar drain) the LDIVH infusion will be discontinued 3-6 hours before performing the procedure then resumed at least 3-6 hours after the procedure is completed if there were no bleeding complications associated with the procedure. For all ventricular drain placements or ventricular drain repositioning a new head CT will need to be obtained that shows no hemorrhagic complication prior to restarting the LDIVH. If there is a new asymptomatic intracranial hemorrhage related to ventricular drain insertion or positioning, then a follow-up head CT will need to be obtained 12 hours later. If the hemorrhage is stable on follow-up head CT then the LDIVH infusion can be resumed.
- Suspensions in administration of the LDIVH will be noted, and an adverse event/adverse drug reaction form will be completed if the drug is held due to hemorrhagic complication.
- LDIVH infusion can be resumed 12 hours after craniotomy assuming a head CT following craniotomy shows no concern.
- Resumption of LDIVH after any other procedures will wait a minimum of 3 hours.

All interruptions of the study drug infusion will be documented on the appropriate CRF. This will include the date of the interruption, the duration of the interruption, the reason for the interruption, and the rate of infusion at which the study drug was resumed.

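### The between-arm CSF hsCRP peak compares post-randomization, drain-dependent subsets with possibly unequal sample counts, so it can differ with no drug effect

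*Protocol*

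**What the plan says.** The Study Synopsis (Section 1.1) defines the primary biomarker endpoint, listed among the secondary endpoints, as "Peak and Overall Plasma and CSF levels of hsCRP at enrollment and, infusion days #2, 4, 6, and 10 compared between groups". Lower CSF biomarker levels under LDIVH are also a secondary objective (Section 1.2.2). The success statement in the synopsis offers two routes on the benefit side: a better mean MoCA score, "or a significant reduction in inflammatory biomarker levels in the LDIVH arm compared to the control arm".

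Section 6.7 makes baseline CSF conditional: "If the subject already has an external ventricular drain or a lumbar drain placed, then removal of cerebrospinal fluid should be performed". Section 6.11 repeats the condition for the later core-laboratory samples: "Additional blood and CSF (when a drain is present) will be drawn at enrollment and post-enrollment days # 2, 4, 6 and 10". Its sentence on hsCRP, "hs-CRP levels will be measured in the CSF as well", does not restate the condition, but no study lumbar puncture or other source of CSF is described. The same section later speaks as if CSF from every patient at every time point will reach the core laboratory, which drain-dependent sampling cannot supply.

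Treating staff know the allocation (Section 5.4), and care otherwise follows local practice (Section 6.12). For minor CNS procedures, including drain placement, Section 9.1 adds in the LDIVH arm that "the LDIVH infusion will be discontinued 3-6 hours before performing the procedure then resumed at least 3-6 hours after the procedure is completed". Ventricular drain placement or repositioning also needs a head CT without hemorrhagic complication before restart. Randomization is stratified by sex and ACoA location only (Section 6.4).

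**The concern.** Having CSF on days 2 to 10, and on how many of those days, is a post-randomization event. It depends on decisions by staff who know the arm, and for new or repositioned drains on steps that apply to one arm only. Subjects with CSF on days 6 and 10 are therefore not a randomized comparison.

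The peak adds a second difficulty. A maximum tends to grow with the number of values it is taken over, so unequal sample counts can separate the arms even when marker levels have the same distribution.

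At stake is the CSF half of the primary biomarker endpoint. The success statement does not say which fluid its biomarker reduction refers to, so a CSF result could be offered in support of it.

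**Working it through.** The protocol states no sample size, power or expected difference for any CSF endpoint, so it has no figure of its own to reproduce. The check asks what the peak does when the drug has no effect.

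**Inputs from the protocol.** 44 per arm (Section 10.1); at most five CSF samples per subject (enrollment and days 2, 4, 6, 10); 5% level with a two-sample t or rank-sum test (Section 10.4). Section 10.4 does not name a side; a two-sided t test is used here.

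**Assumptions, not in the protocol.** Half of each arm drained (0.5 × 44 = 22); levels in SD units; within-patient correlation ρ of 0.5 or 0.7; flat time course; a subject with k samples has the first k of the schedule, as when a drain is removed.

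**Step 1: expected peak.** For k equally correlated standard normal values, E[max] = √(1 − ρ) × E[max of k independent values]. The independent values for k = 1 to 5 are 0, 0.56, 0.85, 1.03 and 1.16.
- ρ = 0.5 (factor 0.707): 0, 0.40, 0.60, 0.73, 0.82 SD.
- ρ = 0.7 (factor 0.548): 0, 0.31, 0.46, 0.56, 0.64 SD.

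**Step 2: false finding of lower LDIVH peaks.** Simulated with 22 versus 22, no drug effect, 20,000 trials; nominal 2.5%. Differences are from unrounded values.

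| Samples, LDIVH v control | Mean difference, ρ 0.5 / 0.7 (SD) | False lower-LDIVH rate, ρ 0.5 / 0.7 |
|---|---|---|
| 5 v 5 | 0 / 0 | about 2.5% / 2.5% |
| 4 v 5 | −0.09 / −0.07 | 6% / 4% |
| 3 v 5 | −0.22 / −0.17 | 13% / 9% |
| 2 v 5 | −0.42 / −0.33 | 34% / 21% |

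If counts vary within each arm around means of about 3 and 4, the rate is 6 to 8%.

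**Step 3: dependence on the time course.**
- Early peak (assumed means 0, 1.5, 1, 0, −1 SD over the five times): 3 v 5 is about nominal, because the missed days rarely hold the maximum. Even then 2 v 5 gives 6 to 9%, since day 4 is lost.
- Later rise (assumed means 0, 0.5, 0.8, 0.8, 0.4 SD): 3 v 5 gives roughly 11 to 19%.

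**Step 4: selection alone.** Suppose drains go to the sickest subjects, severity correlates 0.5 with the marker, and 40% of one arm but 70% of the other is drained. The mean severity of the top fraction p of a standard normal is φ(z)/p, where z is the cut-off: 0.966 for p = 0.4 and 0.497 for p = 0.7. The arms then differ by 0.5 × (0.966 − 0.497) = 0.23 SD with no drug effect, and about 12% of two-sided 5% tests are falsely positive. Here the arm with fewer drained subjects has the higher levels, so selection can work against the sample-count effect. That is one reason the direction is unknown.

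**The case against.** Several points on the other side are sound.
- Section 9.1 governs placing or repositioning a drain. It says nothing about how long a drain stays in. Drains placed before enrollment, which Sections 4.1 and 6.7 anticipate, are untouched by it. A reader might infer that drains will come out earlier, or stay in longer, in the LDIVH arm; the protocol does not support either.
- A reader might infer that fewer samples always mean a lower peak. That holds only if the missed days could contain the maximum, and the protocol gives no marker time course.
- A one-sided 5% test gives larger figures, 21% for 3 v 5 and 46% for 2 v 5 at ρ = 0.5 (nominal 5%). The protocol states one-sided testing only for mean MoCA and for the rate of MoCA ≤ 20. Fixed counts such as 3 v 5 also separate the arms completely, which is an extreme case.
- The drain condition on days 2 to 10 is written for the core-laboratory markers, while the peak is stated only for hsCRP. The link rests on the absence of any other CSF source.
- The endpoint pairs the peak with an overall level, Section 10.4 allows mixed models for repeated observations, and a statistical analysis plan not at hand may define the CSF analysis set.

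These points limit the size of the problem but do not remove it. The protocol itself fixes the drain-dependent sampling, the peak and the between-group comparison. No later analysis can recover CSF that was never drawn.

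**Conclusion.** The concern holds as a design weakness in the CSF half of the primary biomarker endpoint. The comparison is not protected by randomization, and a maximum over possibly unequal numbers of samples is a poor summary for it.

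Neither size nor direction can be stated from the protocol. The illustrative rates run from about nominal (early-peaking marker, 3 v 5 samples) to 34% (flat course, 2 v 5, ρ = 0.5). They rest on the assumed 22 per arm, correlation, time course and sample imbalance.

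A reader might infer that the whole biomarker objective or the success claim is invalid. The protocol does not support that: plasma sampling does not depend on a drain, and the success statement does not name CSF.

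**What to change.** 1. Make plasma hsCRP the sole primary biomarker endpoint, and name it as the basis of the biomarker route to study success.
2. Keep CSF markers as exploratory. Compare them by assigned arm in subjects who already had a drain at enrollment, and only describe subjects first drained later.
3. Replace the CSF peak with log CSF levels by scheduled day, in a repeated-measures model with arm, day and their interaction and the enrollment CSF value as covariate.
4. State that days after drain removal are assumed missing at random. Removal is still decided after randomization by unblinded staff, so restricting the set does not remove this dependence.
5. Report drain-days and CSF sample counts by arm.

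The cost is endpoint and analysis wording, fewer subjects in the CSF comparison, and possibly one added CRF field for drain dates, since the protocol does not say that these are recorded. No change to clinical care or to the sampling schedule is needed.
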